10.3.2.1 Quantitative Analyses

Building our theoretical framework, we will use structural equation modeling (SEM) to test whether engagement with stigma content predicts changes in stigma-related outcomes over time (e.g., decreases in anticipated HIV stigma), and changes in HIV care outcomes over time (e.g., repeat HIV testing; consistent VS). In these HIV-stratified analyses, we will use latent class analysis to characterize users' engagement in the app. We will estimate the independent contributions of passive and active engagement on both stigma and HIV outcomes, as well as how cumulative engagement in stigma-related discussions influences these outcomes. Key sociodemographic predictors will be included as covariates (e.g., age, time since diagnosis). We will also examine the contribution of specific mediators (e.g., social support) in these models by decomposing the total effects into direct and indirect effects. In exploratory analyses, we will use multigroup SEM analyses to test whether these proposed models differ based on latent classes of users (e.g., active forum contributors vs. lurkers; low, moderate, high engagement). Multigroup analyses allow us to compare the strength and direction of the effect sizes in our models and their overall fit across these engagement groups. Ideal models will have values of .90 or higher among fit indices and values of .06 or lower for RMSEA as acceptable indicators.85 The proposed study has sufficient power to carry out these subsample analyses in our model identification and model testing stages. MacCallum et al.²²⁰ show that power of .80 is achievable with alpha=.05 and 30 degrees of freedom in cross-sectional analyses with a sample of 366 for a close model fit (for df=100 the minimum sample size is 178). Thus, we have ample power for these SEM analyses, even when dividing the sample by HIV status or engagement profile.

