5.0 STUDY PROCEDURES

5.1 Enrollment Procedures

We will enroll a total of 750 participants. Of these participants, 300 will be HIV-negative and 450 will be HIV-positive. After participants are consented, participants will complete a baseline CASI survey and then will be randomized into the Tailored Information-Only Control (Attention Control), Researcher-Created HMP Network (Intervention Arm 1), or HMP with Peer-Referral Network (Intervention Arm 2). Intervention Arm 2 will only have 150 HIV-positive participants randomized to it, as the remaining participants will be peers who are referred by their peers and enroll if eligible. Upon enrollment, all participants will be provided a link to access the HMP app through the Apple App Store or the Google Play Store for Android. Once downloaded, participants will create their app account by entering their email address, creating a username, password, and PIN, entering their mailing address, opting in or out of notifications, and selecting an avatar.

Those randomized in the Tailored Information-Only Control (Attention Control) will be given a streamlined version of the app. They will have access to the Care Locator and Knowledge Center articles and be able to message the Care Navigator. HIV-negative and sero-unknown participants will be able to request HIV home test kits. HIV-positive participants will be sent HemaSpot devices at Baseline, 6 months, and 12 months. They will not have access to the interactive forums, activities, or the Ask and Expert feature.

Those randomized in the Researcher-Created HMP Network (Intervention Arm 1) will have access to the full HMP app, including access to the Arm 1 Forum in which participants will be able to create threads and comment on any threads in the forum, whether moderator- or usergenerated.

Those randomized to the Peer-Referral Network (Intervention Arm 2) will have access to the full HMP app, including access to the Arm 2 Forum in which participants will be able to create threads and comment on any threads in the forum, whether moderator- or user-generated. The only difference between this version and the Intervention Arm 1, is that two thirds of the users (300) that comprise this group are added by peer referral by the 150 participants who were randomized into this arm.

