10.2 Power Estimates

The primary outcome for the proposed trial is stratified by HIV status and defined as *successful* engagement in care. For HIV-positive participants at baseline, we define successful engagement in HIV care as consistent VS across the 12-month trial (per IOM guidelines²¹⁸). For HIV-negative

or sero-unknown at baseline, we define successful engagement in care as participation in routine HIV testing (2 HIV tests with at least 3 months apart from one another, per CDC guidelines²¹⁹). We define power as correctly identifying the difference in the proportions of YBLMT with serospecific engagement in HIV care within 12 months of each intervention arm (2 arms: HMP Stigma with researcher-created network, HMP Stigma with peer-referred network) to the control arm (Information Control), thus powering for 3 independent hypothesis tests. Our sample size calculations are based on pair-wise HIV-stratified comparisons of the 3 groups in terms of proportion of successful engagement using a two-sided significance level of 0.05 altered by the number of comparisons using a Bonferroni adjustment (significance level is 0.017 for 3 comparisons). To have 80% power to detect a minimum effect size (OR=1.9) of successful engagement in care between the 3-arm trial, we will require at least 450 HIV-negative and 450 HIV-positive participants to detect a 17% difference in successful engagement in. In the event of a 20% loss to follow-up, we will have sufficient power to detect an OR=2.1 (18% difference) at alpha=.017. Participants may continue the study even if they miss an assessment intermittently. We will compare those who completed different follow-up interviews with those who did not on key baseline predictors to check for possible sampling bias. Our analysis will use ITT as appropriate.

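### The claim of ample SEM power is not supported by the plan's own minimum sizes when engagement profiles are split within HIV strata; the split by HIV status alone is adequate.

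*Combined protocol and SAP*

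**What the plan says.** Section 10.3.2.1 (Quantitative Analyses, Specific Aim 2) takes its power from a published RMSEA result: "power of .80 is achievable with alpha=.05 and 30 degrees of freedom in cross-sectional analyses with a sample of 366", and "for df=100 the minimum sample size is 178". It describes the test only as one of close model fit. From this it draws two conclusions about divided samples: "The proposed study has sufficient power to carry out these subsample analyses in our model identification and model testing stages" and "Thus, we have ample power for these SEM analyses, even when dividing the sample by HIV status or engagement profile".

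The section makes the analyses HIV-stratified and uses latent class analysis within them to describe engagement. Its examples of classes are contributors against lurkers (two) and low, moderate and high engagement (three). It states no model degrees of freedom, RMSEA values under the null and alternative, class sizes or attrition.

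**The concern.** The section quotes minimum sizes and then asserts that the divided sample meets them, but never sets a subgroup size beside a minimum. When that is done, the subgroups formed by engagement profile within HIV status fall short in most configurations.

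What is at stake is how the Aim 2 results are read. Under the test that reproduces 366 and 178, the null hypothesis is that fit is not close. Low power therefore means that a model that fits well in a small class will often fail to gain support. A reader relying on the power statement could take that failure, or an apparent difference in fit between classes, as a finding about engagement when it reflects class size. Aim 2 is a stated secondary objective (section 2.2), although the class-based models themselves are called exploratory.

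**Working it through.** **Reproducing the plan's minimums.** RMSEA power uses the noncentral chi-square with noncentrality λ = (N − 1) × df × RMSEA², at one-tailed alpha 0.05. The plan gives no RMSEA pair, so pairs were tried for the smallest N with 80% power:

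| Null v alternative RMSEA | df=30 | df=100 |
|---|---|---|
| 0.05 v 0.01 (test of not-close fit) | 367 | 178 |
| 0.05 v 0.08 (usual test of close fit) | 314 | 132 |
| 0 v 0.05 | 329 | 164 |
| 0.05 v 0 | 343 | 168 |

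Only 0.05 v 0.01 matches 366 and 178 (power at N = 366 is 80.0%, so 367 is rounding). It is used below as an assumption.

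**Stratum sizes.** Section 3.2 randomizes 150 HIV-positive participants to each of three arms (450) and 150 HIV-negative or unknown to each of two (300). Section 5.1 adds 300 referred peers, and section 3.2 estimates that half are HIV-negative or unknown.
- HIV-positive: 450 + 150 = 600
- HIV-negative or unknown: 300 + 150 = 450
- After the loss allowed for in section 10.2 ("In the event of a 20% loss to follow-up"): 600 × 0.8 = 480 and 450 × 0.8 = 360

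**Subgroup sizes, assuming equal classes.**
- Two classes: 600/2 = 300 and 450/2 = 225
- Three classes: 600/3 = 200 and 450/3 = 150
- Three classes after 20% loss: 480/3 = 160 and 360/3 = 120

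Unequal classes would make the smallest one smaller.

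**One case in full.** N = 150, df = 30: λ under the null is 149 × 30 × 0.0025 = 11.175, and under the alternative 149 × 30 × 0.0001 = 0.447. The critical value is the 5th percentile of the chi-square with 30 df and noncentrality 11.175. The probability of falling below it with noncentrality 0.447 is 0.297.

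**Single-group power (0.05 v 0.01).**

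| Group | N | df=30 | df=100 |
|---|---|---|---|
| HIV-positive, all arms | 600 | 98% | 100% |
| HIV-negative, all arms | 450 | 91% | 100% |
| HIV-positive, 20% loss | 480 | 93% | 100% |
| HIV-negative, 20% loss | 360 | 79% | 99.8% |
| HIV-positive, two classes | 300 | 67% | 99% |
| HIV-negative, two classes | 225 | 49% | 92% |
| HIV-positive, three classes | 200 | 42% | 87% |
| HIV-negative, three classes | 150 | 30% | 69% |
| HIV-positive, three classes, 20% loss | 160 | 32% | 73% |
| HIV-negative, three classes, 20% loss | 120 | 23% | 54% |

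**Forum arms only.** Of control participants, section 5.1 says: "They will not have access to the interactive forums, activities, or the Ask and Expert feature". If a model of forum engagement uses Arms 1 and 2 only, the HIV-negative stratum is 150 + 150 = 300 (67% at df=30), or 240 after loss (53%). At df=100 these are 99% and 95%.

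**Sensitivity to the test.** With 0.05 v 0.08, three-class groups of 200 and 150 have 58.5% and 45.3% power at df=30, and 95.5% and 86.2% at df=100. Two-class groups of 300 and 225 still miss the 314 needed at df=30.

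**Joint fit.** A multigroup model is fitted to all classes together. With G groups, total sample N and df per group, the usual multigroup RMSEA correction gives λ = (N − G) × (G × df) × RMSEA² / G. For three equal classes and 0.05 v 0.01:

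| Stratum | Total N | 30 df per class | 100 df per class |
|---|---|---|---|
| HIV-positive | 600 | 84% | 99.9% |
| HIV-negative | 450 | 65% | 98% |
| HIV-positive, 20% loss | 480 | 69% | 99% |
| HIV-negative, 20% loss | 360 | 50% | 92% |

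**The case against.** Several points on the other side are sound.

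- **The HIV-status split.** A reader might infer that the plan's minimums contradict this split too. They do not: 600 and 450 exceed both. The one all-arm shortfall, 360 against 366 after loss, costs one point of power.
- **Excluding controls and applying 20% loss.** Both are assumptions. Mediation of an intervention effect needs the control arm, controls can read articles (section 3.3.2), and section 8.2 describes engagement across three arms. The 20% belongs to the primary comparison, and section 8.1 retains participants who miss assessments. The main result uses neither assumption.
- **Unknown df.** At 100 df the two-class splits pass (300 and 225 against 178). The shortfall there depends on a smaller model, and the plan does not say which applies.
- **Joint fitting.** The single-group minimum is an approximation for a multigroup model, and at 100 df per class the joint fit exceeds 80% in every all-arm case above. It does not restore the claim at 30 df per class: only the HIV-positive stratum at full enrolment reaches 80%. The section itself applies single-group figures to the divided sample.
- **Reading the two splits separately.** Three classes of the whole sample would be 1,050/3 = 350, with 77% power at df=30 and 99.8% at df=100. That is a near miss, but the section places the classes inside HIV-stratified analyses.
- **Stakes.** The class-based models are exploratory, and no primary conclusion depends on the sentence. That limits the consequence but does not make the statement correct.

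**Conclusion.** The power statement is wrong as written for engagement-profile splits within HIV strata. With all arms, full enrolment, half of peers HIV-negative and three equal classes, the groups of 200 and 150 have 42% and 30% single-group power at df=30, and 87% and 69% at df=100. Two classes miss 366. Three classes after 20% loss miss both minimums. These percentages rest on the assumed RMSEA pair of 0.05 v 0.01; the comparison of group sizes with 366 and 178 does not.

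Three stronger conclusions are not supported:
- That every profile-by-HIV model is below 80%: the HIV-positive class of 200 reaches 87% at df=100, the class of 150 reaches 86.2% under 0.05 v 0.08, and joint fits can do better.
- That poor models would be accepted because the test could not reject them: that describes a 0.05 v 0.08 test, not the one that yields 366 and 178, and the section judges fit by index cut-offs.
- That classes should be pooled over HIV status: the outcomes differ by serostatus (testing or viral suppression), time since diagnosis is named as a covariate, and the section specifies stratified analyses.

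The HIV-status split stands as adequate. Its reservations concern the HIV-negative stratum at df=30: 79% after 20% loss, and 67% (53% after loss) if only forum-arm participants enter the model.

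**What to change.** In section 10.3.2.1, limit the ample-power statement to the split by HIV status, and say which arms enter each model. For the profile-by-HIV models, replace the assurance with attained power calculated from:
- the degrees of freedom of the planned model;
- the null and alternative RMSEA values, with the test named accordingly (366 and 178 match not-close fit);
- expected class sizes, including the smallest class;
- expected attrition.

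State whether the figure is for a single group or a joint multigroup fit, since the two differ. Label as descriptive any profile-by-HIV model that does not reach 80%.

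The cost is a short calculation, revised wording and a less favourable power statement for exploratory models. Enrolment, data collection and the primary analysis are unaffected.

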10.3.2.2 Qualitative Analyses

Using our latent class analysis of users' engagement profiles (e.g. high/low users, lurkers), we will select a subsample of up to 45 enrolled participants (approximately 5 from control and 20 per each intervention arm) across different sociodemographic and user engagement profiles to complete qualitative evaluation interviews (described above in section 5.4.5) Study staff, under the guidance of [name], will create a codebook of *a priori* and emergent themes including operational definitions of all codes and sample quotations to illustrate how to apply each code. Two study team members will use the codebook to independently code the data while a third team member will review these coded sections and resolve discrepancies. We will use Dedoose and Excel matrices to assist with theme identification, coding textual data, and describing relationships among codes (via code co-occurrence and memoing functions).²²¹ Analysis results will be used in conjunction with participants' survey responses, biological outcomes, and usage profiles to present a mixed methods intervention results analysis.

10.3.3 Specific Aim 3:

Specific Aim 3 is to examine whether changes in intersectional stigma and YBLMT's improvements across the HIV care continuum differ based on the network structure underlying user engagement in the two versions of HMP Stigma. To understand the role of social network dynamics between the two intervention conditions, we will compute social network parameters (e.g., size, density, centrality) for each version using the statnet and igraph packages in R.²²² Paradata indicators of active engagement (e.g., forum replies/likes) and passive engagement

(e.g., reading forum posts) will be used to model threaded engagement networks between users. We will use these structures to describe types of users (e.g., discussion starters, contributors, lurkers), their location within the network (e.g., centrality), the frequency of exchanges between users (e.g., reciprocity), and presence of subgroups (e.g., cliques). Core social network metrics will be computed at the participant-level (e.g., centrality; popularity), as well as by stigma-related topic (e.g., trending, liked). We will use these network parameters to model (1) user engagement in HMP and (2) changes in HIV care continuum outcomes. We will use the general framework of generalized linear mixed models^{101–103} (GLMM) to model these longitudinal outcome trajectories. 110-112 Given that some of our outcomes are binary, some count and some continuous traits they will be treated differently (identity for continuous outcome, logit for binary outcome and natural log for count outcomes). We will use the estimated network parameters as covariates in our models, measuring how network characteristics are associated in differences in outcomes across the two treatment groups. In addition, GLMM also allows us to link YBLMT's individual trajectories with social network changes by adding them as time-varying covariates. For example, one analysis will examine how changes in networks' characteristics effect changes in YBLMT's VS, after adjusting for changes in stigma. These follow a network autocorrelation metric, whereby a term is added to the general model to captures a (weighted) average of peers' outcomes. Exploratory analyses will determine if random effects should be included. Maximum likelihood estimation will be used for fixed effects. To ensure robustness, we will also apply an exchangeable working correlation structure to its corresponding generalized estimating equation model. 104

Note: Any deviations from the analysis plans outlined above or in the sections that follow will be documented and justified in the Statistical Analysis Plan developed for this protocol.

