3.2 Sample Size

Participants self-reporting as HIV positive at baseline will be randomized across the three arms (N=150 per arm). Participants who self-report being HIV negative or serostatus unknown at baseline will be randomized (N=150 per arm) into either the Information-Only Control (Attention-Control) or the Researcher-Created HMP Network (Intervention Arm 1). Given that we are allowing the 150 HIV-positive participants assigned to the Peer-Referral version of HMP (Intervention Arm 2) to invite two peers into their social network, we do not know the baseline HIV prevalence among recruited peers. To avoid a priori assumptions of who will be invited, we estimate that half will be HIV-negative or sero-unknown.

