Peer-referred HMP Network Arm: Participants randomized to Intervention Arm 2 (peer-referred network) will be enrolled into a parallel (but separate) version of HMP Stigma. The only difference between Arm 1 and Arm 2 is that participants in Arm 2 will have a referral feature in their profile that allows them to earn \$20 in e-gift cards if they successfully refer and enroll 2 peers of their choosing (\$10 per peer) in the first 45 days of their study participation. The referral feature will create a customized link for each participant that can be emailed or text messaged to invite peers into the study. 189 Simple instructions will be provided at enrollment and in the app describing how to refer them. Participants may send referral links until two of their peers have screened eligible and enrolled in the study. Participants may send referrals from Day 1 – 45 of their time in the trial. If two of a participant's referred peers successfully enroll within that time window, at that point, the original participant will receive a notice from the study team that they have successfully reached their referral quota and the referral feature will deactivate. their referral incentives and HMP usernames of their referrals within their profile. While they will be able to see whether their peer has enrolled and what username the peer created, they will not receive any information about any of their peers' survey responses, including those who screened ineligible. Referred peers will see the HMP username of their referrer; they will not be eligible to refer their own peers.

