4.3 Recruitment

We will reach the population using social media ads on sites including Facebook, Tumblr, Instagram, BGC Live, Jack'd, Grindr, Scruff, and other comparable social media platforms (see example copy and images in "Recruitment materials.docx"). Final platforms and materials will be developed alongside our YAB. Social media platforms allow us to specify our audience based on socio-demographic characteristics (e.g., age, race/ethnicity) to increase their specificity to our population. Ads will link interested individuals to a Qualtrics screener where they may verify their eligibility, email the team, or locate a toll-free number if they want to talk to a team member about the study. Via co-I [name], we have access to an online registry with over 1,000 U.S. men, many of whom are HIV-positive, who have expressed interest in participating in other HIV-related studies. We will collaborate with online groups (e.g., Young Black Gay Men's Leadership Initiative; Trans Women of Color Collective) and other advocacy groups to post study and recruitment information. We foresee recruiting 25-30 participants per month during Years 2-4; this staggered design will allow us to accommodate the enrollment and testing of YBLMT in the trial and also allow time for the social networks to develop.

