Intervention Arms 1 (Researcher-generated) and 2 (Peer Referred) will operate as two distinct virtual communities. Participants will not be able to communicate across arms and will only be able to view the posts of participants in their Arm.

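### Aim 3: with one closed network per intervention arm, whole-network measures such as size and density cannot be separated from arm and should be descriptive only

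*Combined protocol and SAP*

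**What the plan says.** Specific Aim 3 (10.3.3) asks whether changes in stigma and in the HIV care continuum depend on the network structure of the two versions of the app. The section says "we will compute social network parameters (e.g., size, density, centrality) for each version". It also plans metrics for individual participants and by stigma topic. Network parameters then enter generalized linear mixed models as covariates, with the purpose of "measuring how network characteristics are associated in differences in outcomes across the two treatment groups". Time-varying network covariates, a network autocorrelation term and a GEE check with exchangeable correlation are planned as well.

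On the networks themselves, section 5.1 says that Arms 1 and 2 "will operate as two distinct virtual communities" and that members "will only be able to view the posts of participants in their Arm".

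On how the arms differ, section 3.3.2 says: "The only difference between Arm 1 and Arm 2 is that participants in Arm 2 will have a referral feature". Section 5.1 names a different sole difference, namely that "two thirds of the users (300) that comprise this group are added by peer referral". Sections 3.2, 4.1 and 5.4.1 set out further differences. Arm 1 is half HIV-positive. Everyone randomised to Arm 2 is HIV-positive. Referred peers may be of any race or ethnicity, and their HIV status is not known in advance.

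**The concern.** A covariate can help to explain an arm difference only if it varies in some way that arm does not. With two networks, one per arm, a whole-network summary has two values and therefore carries the same information as the arm indicator. If density or size were entered as an explanatory covariate, the model would either fail to separate it from arm or, with arm left out, relabel the arm difference as a density effect.

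The two communities also differ by design in size, HIV mix and eligibility, and density itself depends on size. Aim 3 could then report that a denser or sparser network accounts for a difference in outcome when the data cannot distinguish structure from size, composition or mode of recruitment.

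**Working it through.** **Inputs.** HIV-positive participants: 150 per arm in three arms (3.2). HIV-negative or unknown: 150 each in control and Arm 1 (3.2). Referral cap: two enrolled peers per index participant (3.3.2). Accrual: "We foresee recruiting 25-30 participants per month during Years 2-4" (4.3), taken here as 36 months. The documents give neither the mean number of ties per user nor the expected referral uptake, so both are varied below.

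**1. Planned sizes.** Control 150 + 150 = 300. Arm 1 150 + 150 = 300. Arm 2 150 + 2 × 150 = 450. The total is 1,050, as in the abstract and 3.1. The randomised total is 300 + 300 + 150 = 750 and the peer share of Arm 2 is 300/450 = two thirds, both as in 5.1. The 450 is a ceiling, because it needs every index participant to enrol two peers.

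**2. Fixed whole-network parameters.** Let arm be 0 or 1 and let D be density, with values d1 and d2. Then D = d1 + (d2 − d1) × arm, an exact function of arm. In the predictor b0 + b1 × arm + b2 × D, only b1 + b2(d2 − d1) can be estimated as the arm contrast. The design matrix [1, arm, density, size] has rank 2, not 4. By contrast, [1, arm, raw participant degree] has full rank, 3 of 3.

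**3. Time-varying whole-network size.** Assume linear entry, so cumulative size at calendar month c is N × c/36. This gives 100 v 150 at month 12, 200 v 300 at month 24 and 300 v 450 at month 36. On the log scale, size is an arm term plus a calendar term and nothing else. Evaluated at every member's 0, 3, 6, 9 and 12-month surveys:

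| Definition of size | R² on arm | R² on arm + calendar month | Same, log size |
|---|---|---|---|
| Cumulative | 0.15 | 0.97 | 0.99 |
| Entered in last 12 months | 0.33 | 0.97 | 0.98 |

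Size is therefore not aliased with arm alone, but almost all of its remaining variation is calendar time. Section 10.3.3 plans no adjustment for calendar time or enrolment date.

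**4. Density.** With mean ties k and n members, density = k/(n − 1). At equal k the Arm 2/Arm 1 ratio is 299/449 = 0.666, or 33% lower; for k = 10 the densities are 0.0334 v 0.0223. If k grows as (n − 1)^a, the ratio is (449/299)^(a − 1):

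| How ties scale with membership | Ratio | Arm 2 lower by |
|---|---|---|
| Equal mean ties (a = 0) | 0.666 | 33% |
| Square root of n − 1 (a = 0.5) | 0.816 | 18% |
| Equal probability per pair (a = 1) | 1.000 | 0% |

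At equal mean ties, by referral uptake:

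| Peers per index participant | Arm 2 size | Ratio |
|---|---|---|
| 2 | 450 | 0.67 |
| 1.5 | 375 | 0.80 |
| 1 | 300 | 1.00 |
| 0.5 | 225 | 1.33 |

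A participant's degree divided by n − 1 inherits the same offset: 0.033 v 0.022 at mean degree 10.

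**5. Composition.** Arm 1 is 150/300 = 50% HIV-positive. If the planning estimate in 3.2 is read as half of 300 peers being negative or unknown, Arm 2 is (150 + 150)/450 = 67% HIV-positive. The possible range at full uptake runs from 150/450 = 33% to 450/450 = 100%.

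**The case against.** The strongest reply is that the plan already contains the sound analysis. Section 10.3.3 lists participant-level metrics and then says that these network parameters will be modelled. Nowhere does it state that density or size enters an outcome model. A reader might infer that it certainly does; the documents do not establish that. What stands is that the covariates are left unspecified directly after whole-network parameters have been listed for computation, so the invalid use is open.

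A reader might also infer that Aim 3 as a whole cannot be estimated. It can be, at participant level, and time-varying covariates do break exact aliasing. The 97% in step 3 depends on assumed linear accrual.

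It is tempting to say that density must differ by a third even when behaviour is identical. That needs equal mean ties and full referral uptake. Members may comment on any thread in their arm's forum, so ties that grow with membership are plausible, and referral is optional.

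Staggered entry invites a further claim, that many pairs of members were never in the study together. With even entry over 36 months and activity ending at 12 months, the share would be (1 − 12/36)² = 44%. The plan specifies neither a cumulative network nor an end to activity at 12 months. It also counts reading posts as engagement, so a later entrant may be able to connect with an earlier member's post. The figure is not evidence against the plan as written.

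Finally, differing composition is the declared contrast (5.4.1), the sole-difference sentence in 3.3.2 can be read as describing app features, and much of the Aim 3 language is associational. That is fair, but the section also describes network changes as producing changes in viral suppression, and the two sole-difference statements do not agree with each other.

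**Conclusion.** The point holds in a limited form. Any fixed whole-network parameter is fully aliased with arm; this follows from the design and needs no assumption about behaviour. Time-varying versions add little beyond arm and calendar time if accrual is roughly linear. Participant-level metrics are estimable, although up to 300 of the 450 in Arm 2 are not randomised, so their associations are not protected by randomisation.

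The size of the density artefact is not known. At full uptake it lies between 0% and 33% under the tie models shown. At equal mean ties it vanishes at one peer per index participant and reverses below that. This dependence on recruitment yield is itself a reason not to read density as behaviour.

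The sole-difference statements in 3.3.2 and 5.1 conflict with 3.2, 4.1 and 5.4.1. The change should be made, but Aim 3 is secondary and the primary analysis in 10.3.1 uses no network parameter.

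**What to change.** 1. In 10.3.3, report whole-network size, density and centralisation as descriptive only, and exclude them as explanatory covariates in the Arm 1 v Arm 2 outcome models.
2. Base network inference on the participant-level metrics already planned. Compute them in fixed windows from the timestamped paradata, include enrolment date as a covariate, and report raw degree beside any size-normalised metric, because normalising by membership brings the size offset back.
3. Reconcile the sole-difference wording in 3.3.2 and 5.1 with the stated differences in planned size, HIV mix and peer eligibility. Word the Aim 3 conclusion as a comparison of two communities, not as an effect of network structure.

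The cost is protocol wording and analysis code, with no new data. The downside is a narrower Aim 3 claim.
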